### **5.2.5 Schwab and England ADL Scale (Patient and Caregiver Versions)**

The Schwab and England ADL scale is an assessment of an individual's ability in activities of daily living, rated in 10% increments where 100% = completely independent, and 0% = vegetative. The scale will be completed independently by both the subject and the caregiver. Missing scores will not be imputed.

### **5.2.6 MDS-UPDRS Parts I and II (Patient and Caregiver Version)**

The MDS-UPDRS is a comprehensive battery of motor and behavioral indices. The MDS-UPDRS Parts I and II will be used to assess non-motor aspects of experiences of daily living (Part I) and motor aspects of experiences of daily living (Part II).

#### **5.2.6.1 MDS-UPDRS Part I**

Part I of the MDS-UPDRS assesses the non-motor aspects of experiences of daily living. Part I consists of 13 items: cognitive impairment, hallucinations and psychosis, depressed mood, anxious mood, apathy, features of dopamine dysregulation syndrome, sleep problems, daytime sleepiness, pain and other sensations, urinary problems, constipation problems, light headedness on standing, and fatigue. The first 6 items are assessed by the investigator (with input from patients or caregivers), and the last 7 items are completed by the patient with or without the aid of a caregiver.

Each item is scored on a 5-point Likert scale: 0 = normal, 1 = slight, 2 = mild, 3 = moderate, 4 = severe.

The total score will be derived as the sum of the 13 individual items from Part I. If 1 or 2 items are missing, the total score will be imputed as the mean of the non-missing items multiplied by 13 and rounded to the nearest integer. If more than 2 items are missing, the total score will be set to missing.

#### **5.2.6.2 MDS-UPDRS Part II**

Part II of the MDS-UPDRS concerns the motor aspects of experiences of daily living. Part II consists of 13 items: speech, saliva and drooling, chewing and swallowing, eating tasks, dressing, hygiene, handwriting, doing hobbies and other activities, turning in bed, tremor, getting out of bed (or a car or a deep chair), walking and balance, and freezing. All 13 items are completed by the patient with or without the aid of a caregiver.

Each item is scored on a 5-point Likert scale: 0=normal, 1=slight, 2=mild, 3=moderate, 4=severe.

The total score will be derived as the sum of the 13 individual items from Part II. If 1 or 2 items are missing, the total score will be imputed as the mean of the non-missing items multiplied by 13 and rounded to the nearest integer. If more than 2 items are missing, the total score will be set to missing.

### **5.2.7 CGI-S for Hallucinations and Delusions**

The CGI-S is a single-item, clinician-rated, 7-point scale that is designed to rate the severity of the subject's hallucinations and delusions at the time of assessment using Investigator's judgment and past experience with subjects who have the same disorder. The 7-point scores are: 1=normal, not at all ill; 2=borderline mentally ill; 3=mildly ill; 4=moderately ill; 5=markedly ill; 6=severely ill; 7=among the most extremely ill patients. Higher scores denote more severe symptoms of hallucinations and delusions. Missing CGI-S scores will not be imputed.

### **5.2.8 CGI-I for Hallucinations and Delusions**

The CGI-I is a clinician-rated, 7-point scale that is designed to rate the total improvement in the subject's hallucinations and delusions at the time of the assessment, relative to the symptoms at Baseline. The 7-point scores are: 1=very much improved; 2=much improved; 3=minimally improved; 4=no change; 5=minimally worse; 6=much worse; 7=very much worse. Higher scores denote more severe symptoms of hallucinations and delusions. Missing CGI-I scores will not be imputed.

### **5.2.9 PGI-I for Hallucinations and Delusions**

The PGI-I is a single-item, global index used to rate the patient's impression of response of a condition to a therapy. The PGI-I asks the patient to rate their symptoms (of hallucinations and delusions) now, as compared with how it was at Baseline before beginning treatment, according to a 7-point scale. The 7-point scores are: 1=very much improved; 2=much improved; 3=minimally improved; 4=no change; 5=minimally worse; 6=much worse; 7=very much worse. Missing PGI-I scores will not be imputed.

### **5.2.10 Virtual Reality Functional Capacity Assessment Tool**

The Virtual Reality Functional Capacity Assessment Tool (VRFCAT) is a tablet-based assessment of functional capacity that simulates key instrumental activities of daily living in a realistic and interactive virtual environment. It will be used to explore the effects of pimavanserin on functional capacity and cognition. VRFCAT tablets will be provided by

VeraSci. The specific VRFCAT software utilized in this study are Pathway version 1.16.15 and software build 20200206.1

Study participants are asked to complete 12 objectives associated with multiple components of a shopping trip, including searching the pantry, making a shopping list, taking the correct bus to the store, shopping, paying for purchases, and getting home (see Table 1). Two different versions of the 4 mini scenarios are utilized in this study. Each version has a unique recipe, unique bus fares, and unique amounts of money in the wallet.

**Table 1 VRFCAT Mini Scenarios and Objectives**

Mini Scenario	Objective	Description
Apartment	1	Pick-up the recipe on the counter
	2	Search for ingredients
	3	Cross off ingredients and pick up bus schedule
	4	Pick up wallet
	5	Exit the apartment
Bus to Store	6	Board the bus to grocery store
Store	7	Pay for the bus
	8	Select food aisle
	9	Shop for groceries
	10	Pay for groceries
Bus to Apartment	11	Board the bus for home
	12	Pay for the bus

For each objective, participants who are unable to complete the objective within a pre-specified time period or who make too many errors are automatically progressed (i.e., forced progression) to the next objective.

For each objective the VRFCAT derives the following quantities:

- 1) Adjusted time (msec): Time to complete an objective, corrected for time of forced inactivity when an error occurs (as well as other factors). For example, if a subject makes an error, an error message is given during which the subject is not able to

proceed. The time required for the error message to display is removed from the adjusted time.

2) Forced progression: Progressions are scored using a binary value, such that 1 indicates the subject was progressed to the next objective at least once in a given testing period because the current objective was not completed in a timely manner.

3) Error count: total number of errors for a given objective.

The total adjusted time, total forced progressions, and total errors are then calculated as the sum of the adjusted time, forced progression, and error count, respectively, across all 12 objectives. Adjusted times will be converted from msec to seconds for purposes of analysis.

The VRFCAT software then takes the total adjusted time, total errors, and total forced progression scores and transforms them into T-scores according to the following algorithm:

1) calculate Z-score using age and sex corrected mean and standard deviation values from Verasci's proprietary normative data, i.e.

$$\text{Z-score} = -1 \times (\text{raw value} - \text{normative\_mean}) \div \text{normative standard deviation}$$

2) calculate T-score as  $(\text{Z-score} \times 10) + 50$

Missing scores will not be imputed for any of the VRFCAT variables.

### **5.2.11 Caregiver Strain Index**

The Caregiver Strain Index (CSI) is a 13-item questionnaire that measures strain related to care provision, and can be used to quickly identify families with potential caregiving concerns. There is at least one item for each of the following major domains: employment, financial, physical, social and time. Positive responses to seven or more items indicate a greater level of strain. Each item is scored zero (answered no) or one (answered yes). The total score is the sum score of the 13 items, resulting in a minimum possible score of 0 (no strain) and a maximum possible score of 13 (maximum possible strain). A score of 7 or higher indicates a high level of stress.

If 1 or 2 items are missing, the total score will be imputed as the mean of the non-missing items multiplied by 13 and rounded to the nearest integer. If more than 2 items are missing, the total score will be set to missing.

### **5.2.12 Geriatric Depression Scale (Short Form)**

The Geriatric Depression Scale (GDS) (Short Form) is a brief 15-item questionnaire in which participants are asked to respond by answering yes or no in reference to how they felt over

the past week. For items 1, 5, 7, 11, and 13 a “no” response is scored as 1, and a “yes” response as 0. For items 2, 3, 4, 6, 8, 9, 10, 12, 14, and 15 a “yes” response is scored as 1, and a “no” response is scored as 0.

The GDS total score will be calculated as the sum of the 15 item scores. A total score of  $\geq 5$  suggests depression.

If 1 or 2 items are missing, the total score will be imputed as the mean of the non-missing items multiplied by 15 and rounded to the nearest integer. If more than 2 items are missing, the total score will be set to missing.

### 5.3 Analysis Visit Windows

Baseline is defined as the last non-missing value, including results from repeated and unscheduled measurements, prior to the first dosing of study drug. The first dose date is defined as the date of the first dose of study drug. Efficacy and safety assessments will be summarized by analysis visit as presented in Table 2 below, excluding Follow-up.

**Table 2 Analysis Visit Windows**

Analysis Visit Name	Target Study Day 	Study Day Interval
Baseline	1	$\leq 1$
Week 2	15	2 - 21
Week 4	29	22 - 43
Week 8	57	44 - 71
Week 12	85	72 - 99
Week 16	113	100 - 127
Follow-up	141	128 to maximum

 If the assessment date  $\geq$  first dose date, study day = assessment date - first dose date + 1, otherwise study day = assessment date - first dose date. Study day 1 is the day of first dose.

#### 5.3.1 Unscheduled Assessments

Both scheduled and unscheduled assessments, including early termination visits, will be considered for planned timepoint summaries, unless noted otherwise. All assessments will be presented in data listings.

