3 STUDY DESCRIPTION

3.1 Overview of Study Design

This study will be conducted as a 16-week, multi-center, single-arm, open-label study. Pimavanserin (ACP-103) will be administered at a dose of 34 mg to approximately 50 subjects with PDP. Approximately 89 subjects with PDP will be screened and 53 subjects are expected to be enrolled, assuming a screen failure rate of 40%. Approximately 42 subjects are expected to complete the study, assuming a 20% drop-out rate. Approximately 25 sites in the US will participate in this study.

The duration of participation for individual study subjects will be up to 26 weeks, consisting of the following 3 periods ([Figure S-1](#)):

- Screening period (3-35 days)
- Treatment period (16 weeks)
- Safety follow-up period (30-34 days).

The study will be conducted on an outpatient basis with visits performed at Screening, Baseline (Week 0), Week 2, Week 4, Week 8, Week 12, Week 16 (end of Treatment Period) and Follow-up (at least 30 days and not to exceed 34 days after last dose of study drug).

The study start date is defined as the date the first subject is enrolled, which is the baseline visit date for the first subject. The primary completion date is the last date that subject data was collected for the primary outcome measure. The study completion date is defined as the last date that subject data was collected, which includes the safety follow-up telephone call visit.

Procedures for when a subject is lost to follow-up are provided in [Section 4.5](#).

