9.5.1 Primary Analyses

The primary efficacy endpoint, change from baseline to Week 16 in the mFSQ total score, will be evaluated using a mixed-effects model for repeated measures (MMRM). The response variable is the change from Baseline to Weeks 4, 8, 12, and 16 and the fixed effects include visit (Weeks 4, 8, 12, and 16), corresponding Baseline score, and the Baseline score-by-visit interaction. The mFSQ total score will be calculated as the unweighted mean of the subscale scores (Basic ADL, Intermediate ADL, Psychological Function, Social Activity and Quality of Social Interaction). The Work Performance subscale will be excluded, given the age and non-employment status of the intended patient population.

Summary statistics for the mFSQ total score (observed and change from Baseline), least-squares (LS) means and the corresponding 95% CI will be presented.

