9.5.3 Exploratory Analyses

The change from Baseline to Week 16 in the exploratory endpoints measured at scheduled visits, including individual mFSQ subscales, Caregiver Strain Index total score, NPI-Q Nighttime Behavior domain severity and caregiver distress, Geriatric Depression Scale (Short Form), and the VRFCAT (total time to complete, total number of errors, and total number of forced progressions), will be summarized using an MMRM model similar to that described for the primary analysis, except that 1) the Baseline value of the endpoint being analyzed will be included in the model instead of the Baseline mFSQ total score; and 2) VRFCAT is not

assessed at Weeks 2, 8, and 12, thus the model will only include Weeks 4 and 16. Additional exploratory analyses may be conducted on the VRFCAT data to adjust for deficits of cognition.

In addition to the Week 16 timepoint, each of the primary, secondary, and exploratory endpoints will also be assessed at all other timepoints (Weeks 2, 4, 8, and 12) using the MMRM models described in [Sections 9.5.1, 9.5.2, and 9.5.3](#). These additional timepoints will be considered exploratory.

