### 3 STUDY DESIGN

#### 3.1 General Study Design

This study will be conducted as a 16-week, multi-center, single-arm, open-label study. Pimavanserin (ACP-103) will be administered at a dose of 34 mg to approximately 53 subjects with PDP. Approximately 42 subjects are expected to complete the study, assuming a 20% drop-out rate. Approximately 25 sites in the US will participate in this study.

The duration of participation for individual study subjects will be up to 26 weeks, consisting of the following 3 periods:

[figure not shown]
- Screening period (3-35 days)
- Treatment period (16 weeks)
- Safety follow-up period (30-34 days)

The study will be conducted on an outpatient basis with visits performed at Screening, Baseline (Week 0), Week 2, Week 4, Week 8, Week 12, Week 16 (end of Treatment Period) and Follow-up (at least 30 days and not to exceed 34 days after last dose of study drug). The first dose of study drug (pimavanserin) should be taken on the morning of the day after the Baseline visit.

The study start date is defined as the date the first subject is enrolled, which is the baseline visit date for the first subject. The primary completion date is the last date that subject data was collected for the primary outcome measure. The study completion date is defined as the last date that subject data was collected, which includes the safety follow-up telephone call visit.

[Figure 1](#) illustrates the study design.

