### **3.5 Determination of Sample Size**

This is an exploratory study and is not powered for statistical significance. Formal sample size calculations were not used to determine sample size.

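### One visit-window table for every scale labels early-termination mFSQ values from Days 2-21 as Week 2, outside the primary model

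*SAP*

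**What the plan says.** **Windows.** SAP 5.3 applies one table to everything: "Efficacy and safety assessments will be summarized by analysis visit as presented in Table 2 below, excluding Follow-up". Table 2 gives Week 2 as Days 2-21, Week 4 as 22-43, Week 8 as 44-71, Week 12 as 72-99 and Week 16 as 100-127. SAP 5.3.1 adds: "Both scheduled and unscheduled assessments, including early termination visits, will be considered for planned timepoint summaries, unless noted otherwise". I found no window specific to a scale and no rule that reassigns ET values.

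**Schedule.** The schedule of events (Protocol Table S-1, SAP 20.2) asks ET subjects for all Week 16 assessments where possible, so the FSQ and VRFCAT can be collected on any day. The FSQ is not scheduled at Week 2. The VRFCAT is not scheduled at Weeks 2, 8 or 12.

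**Models.** In Protocol 9.5.1, "the fixed effects include visit (Weeks 4, 8, 12, and 16" lists the primary visits. For VRFCAT, Protocol 9.5.3 says "thus the model will only include Weeks 4 and 16". The same section then states that each primary, secondary and exploratory endpoint "will also be assessed at all other timepoints (Weeks 2, 4, 8, and 12", with the same models. SAP 12.8 specifies an effect for visit without listing levels. It uses an unstructured covariance and offers only descriptive statistics if the fit does not converge. SAP 18 declares no change from the protocol.

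**Analysis set.** SAP 4.2 admits a subject to the Full Analysis Set on any post-baseline mFSQ value, whatever its day.

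**The concern.** The windows follow the visit calendar, not the calendar of each scale. Barring an unscheduled FSQ, an mFSQ value on Days 2-21 can come only from an early terminator, and it is that subject's only post-baseline value. Under the protocol's visit list the subject is in the analysis set with no record in the primary model. SAP 12.4 relies on that model to handle missing data, so the plan collects a dropout's value and then leaves it out of the analysis meant to deal with dropout. The LOCF t-tests could use it, so the two analyses may rest on different subjects.

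The Week 2 sentence in Protocol 9.5.3 also asks for an estimate that the schedule cannot supply. SAP 12.8 does not tell the programmer whether Week 2 is a level. In an open-label study, that choice should not be left until the data are visible.

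**Working it through.** **1. The plan's own figures.** Enrolment: 89 × (1 − 0.40) = 53.4, which agrees with the 53 in Protocol 3.1. Completion: 53 × (1 − 0.20) = 42.4, which agrees with SAP 3.1 ("Approximately 42 subjects are expected to complete the study, assuming a 20% drop-out rate"). Early terminators: 53 − 42 = 11. Midpoints of adjacent target days 15, 29, 57, 85, 113 and 141 are 22, 43, 71, 99 and 127. These reproduce the limits in Table 2, with Day 22 going to the later window and the other midpoints to the earlier one.

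**2. Where ET values fall.** The documents do not give dropout timing, so I assumed four patterns over Days 2-112, with all 11 subjects completing the FSQ and VRFCAT at ET. For the uniform pattern:
- Days 2-21: 20/111 = 0.180, and 11 × 0.180 = 2.0 mFSQ values in Week 2. P(at least one) = 1 − (91/111)^11 = 0.89.
- VRFCAT in the Week 2, 8 and 12 windows: (20 + 28 + 28)/111 = 0.685, and 11 × 0.685 = 7.5 values.

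| Assumed dropout pattern | Share on Days 2-21 | mFSQ values outside primary model | P(at least one) | VRFCAT values outside its model |
|---|---|---|---|---|
| Uniform | 0.180 | 2.0 | 0.89 | 7.5 |
| Early, exponential, mean 28 days | 0.520 | 5.7 | 1.00 | 7.9 |
| Early, exponential, mean 56 days | 0.348 | 3.8 | 0.99 | 7.6 |
| Late, rising linearly | 0.036 | 0.4 | 0.34 | 7.4 |

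If only half of early terminators complete the scales, the expected counts halve; the uniform mFSQ count becomes 2.0 × 0.5 = 1.0.

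**3. Which VRFCAT subjects still contribute.** Under uniform dropout, 11 × 56/111 = 5.5 of the 7.5 affected subjects leave on Days 44-99. They would normally keep their scheduled Week 4 value and lose only the last one. The other 2.0 have no VRFCAT value in the model. With the steepest early pattern the split reverses: 11 × (0.144 + 0.053) = 2.2 keep a Week 4 value and 5.7 do not.

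**4. If Week 2 were entered as a level of the primary model.** I simulated 53 subjects with five visits, an unstructured covariance (15 parameters) and a mean and baseline slope per visit (10 parameters). Week 2 was seen only in k early terminators, who have no later value.
- k = 1: fixed-effect rank 9 of 10. The Week 2 mean and slope cannot both be estimated.
- k = 2: full fixed-effect rank, but no residual degrees of freedom for the Week 2 variance. The restricted-likelihood Hessian has rank 10 of 15.
- k = 3 or 5: Hessian rank 11 of 15. The four covariances of Week 2 with Weeks 4, 8, 12 and 16 carry no information.
- For k = 2, 3 and 5, at the same covariance values, the Week 16 coefficients are identical with and without the Week 2 records. No subject contributes to both parts, so the likelihood factorises.

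**5. The same midpoint rule applied to the FSQ schedule.** Target days 29, 57, 85 and 113 give Week 4 = Days 2-43, with Weeks 8, 12 and 16 unchanged. No mFSQ value up to Day 127 then falls at an unscheduled visit.

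**The case against.** The strongest reply is that the primary model is already fixed. The protocol synopsis and 9.5.1 list Weeks 4, 8, 12 and 16, and SAP 18 changes nothing. The Week 2 sentence in 9.5.3 is a catch-all: the same section restricts VRFCAT to two visits, so the sentence cannot override endpoint-specific lists. This stands. A reader might infer that stray Week 2 values make the primary model inestimable, but the documents do not support that. It requires Week 2 to be added against 9.5.1, and even then the Week 16 mean stays identified. What remains is a risk of non-convergence, or of a singular information matrix for the Kenward-Roger adjustment, with only descriptive statistics to fall back on.

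A reader might also infer that dropout data are lost. That too goes further than the text. ET mFSQ values from Day 22 fall at modelled visits, and the earlier ones are listed and not barred from the LOCF t-tests.

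It is also fair that the counts rest on assumed timing and full completion, when the schedule requires only safety assessments at ET. VRFCAT is exploratory and has no bearing on the primary model. Finally, the SAP says of the study: "This is an exploratory study and is not powered for statistical significance". These points limit the size of the problem but do not supply the missing rule.

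**Conclusion.** The point holds as a gap in the window rules. Followed literally, the SAP puts a subject with a Day 2-21 ET mFSQ into the Full Analysis Set with no record in the primary model, and Protocol 9.5.3 promises a Week 2 mFSQ estimate that the schedule cannot support. The expected size is about 2 of 53 subjects under uniform dropout, or 0.4 to 5.7 over the patterns tried, if all 11 early terminators complete the scales. The effect on the Week 16 estimate cannot be computed, because the documents give no standard deviation or expected effect. For VRFCAT, 7.4 to 7.9 of 11 ET values miss the model. Under uniform dropout most of those subjects keep their Week 4 value. The mFSQ part should be corrected before database lock; the VRFCAT part is secondary.

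**What to change.** 1. **SAP 5.3:** set the mFSQ Week 4 window to Days 2-43 and leave the other mFSQ windows as they are.
2. **SAP 12.8:** list the visit levels for these models: mFSQ at Weeks 4, 8, 12 and 16; VRFCAT at Weeks 4 and 16.
3. **Protocol 9.5.3 and the SAP by-visit analyses:** remove Week 2 for mFSQ, including from the t-tests, and record the change in SAP 18.
4. **VRFCAT:** midpoint windows (Week 4 = Days 2-71, Week 16 = Days 72-127) are not enough. The closest-to-target rule in SAP 5.3.2 would still drop an ET value on Days 44-71 when a scheduled Week 4 value exists. If these values are to be used, pre-specify that an ET value goes to that scale's next scheduled visit.

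The cost is a few lines of text, and some early values carry a later label. A Day 2 mFSQ labelled Week 4 is 29 − 2 = 27 days before target. Under the VRFCAT rule a Day 44 value labelled Week 16 is 113 − 44 = 69 days before target. That is a real compromise at the endpoint visit, so using the VRFCAT values is a judgement for the sponsor.
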